9.1 Study design

This is a population-based retrospective cohort study designed to assess the characteristics of patients and patterns of drug utilization in new users of DOACs in the UK.

The study enrollement period extends from 1st January 2011 up to last available database extraction (at time of writing, May 2016 in THIN and in CPRD).

Among the source population resulting from the combination of THIN and CPRD databases, we will ascertain three separate cohorts of first-time users of rivaroxaban, apixaban and dabigatran using the date of first prescription (index date) of the respective drug (index drug).

This study will apply a new-users (initiators) design (Ray et al, 2003). New users are individuals starting a study medication for the first time ever recorded in the database. Yet, they may have used the other study medications before index date and therefore classified as non-naïve. New-users without any history of any oral anticoagulant would be classified as naïve.

All patients aged 18 and above and who have been enrolled in the databases for at least 1 year and had their first prescription recorded in the databases at least 1 year ago will be included in source population. A patient will be considered eligible to enter a study cohort as a first-time user of one the study drugs when he or she has a first prescription of the drug recorded during the enrolment period.

Patients who have any record of being prescribed their index drug prior to the enrolment period or who qualify as members of more than one cohort on the same day, will be excluded. If a patient qualifies as first-time user of more than one study drug during the enrolment period, with different index dates, she/he will be assigned to the cohort of study drug first prescribed during the enrolment period, with the date of this prescription being the index date. (eg mutually exclusive cohorts)

Among the three study cohorts, we will further identify patients with NVAF defined as:-

Patients with a record of Atrial fibrillation (AF) any time prior index date or within the 2 weeks after the index date, and free of valvular replacement or mitral stenosis prior to index date or 2 weeks after index-date

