9.3 Variables

The following variables will be collected among the three study cohorts of DOACs:

- age and sex distribution at index date;
- dose of index drug at index date, dose posology, and duration of treatment (including pack size);
- type and duration of other anticoagulant use before the index date
- prior anticoagulation (DOACs, warfarin and LMWH) before index date: proportion of naïve patients (defined as those with no use of any anticoagulant ever prior to index date)
- use of specifically prescribed medications both in the year before the index date and year after the index date: antiplatelet drugs (low-dose acetylsalicylic acid, clopidogrel, dipyridamole, prasugrel, ticlopidine and ticagrelor); anticoagulants (including rivaroxaban, dabigatran, apixaban, warfarin, and LMWH), antiarrhythmic drugs, antihypertensive drugs, statins, anti-diabetic agents, non-steroidal anti-inflammatory drugs, oral steroids, acid-suppressive drugs, disease-modifying anti-rheumatic drugs, antidepressants, antipsychotic drugs, oral contraceptives, hormone-replacement therapy, strong inhibitors of either cytochrome P450 3A4 or P-glycoprotein (e.g. the systemic azole antimycotics ketoconazole, itraconazole, voriconazole and posaconazole and the HIV-protease inhibitor ritonavir), strong CYP3A4 inducers (e.g. rifampicin, phenytoin, carbamazepine or phenobarbital) and fluconazole.
- Renal disease (estimated glomerular filtration rate (eGFR) before index date as well as ACR (Albumin/Creatinine Ratio) where available.
- Comorbidity: haemorrhagic disease and history of intracranial haemorrhage, urogenital bleeding and gastrointestinal bleeding. Liver disease, pancreatic disease, cancer, cardiovascular disease (acute MI, coronary artery disease, congestive heart failure, ventricular arrhythmia, peripheral arterial disease) cardiovascular risk factors (hypertension, diabetes mellitus, hyperlipidaemia and obesity), stroke/TIA, respiratory disease (asthma and chronic obstructive pulmonary disease), rheumatoid arthritis, osteoarthritis, gastrointestinal disease, liver disease and pancreatic, alcohol-related disorders.

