- CHADS₂ and CHA₂DS₂-Vasc scores will be calculated based on the presence/ history of congestive heart failure, hypertension, age, diabetes mellitus and prior stroke or transient ischaemic attack. HAS-BLED score for major bleeding risk (hypertension, renal disease, liver disease, stroke history, prior major bleeding or predisposition to bleeding, age > 65, medication usage predisposing to bleeding, alcohol usage history), will also be calculated .

- smoking status, body mass index (BMI) and Townsend score: most recently recorded value before the index date.
- healthcare utilization in the year prior to the index date and the year after (e.g. PCP visits, outpatient visits and hospital admissions).

Parameter	Description/ Definition
Demographic Characteristics at index date	
 • Age • Sex • Smoking status (previous 6 months) • Body mass index (previous 6 months) • Blood pressure history (previous 12 months) • Number of patients that are naïve vs non-naïve • For non-naïve: type and duration of anticoagulant used before index date
Risk factor categories	
 • CHADS₂ score • CHA₂DS₂ VASC • HASBLED score • INR measurement
Previous medical history (12 months prior to index date)	
 • Acute MI • Stroke or TIA • Systemic peripheral arterial embolism • Coronary artery disease • Congestive heart disease • Hypertension • Diabetes • Renal disease (eGFR) or ACR (Albumin/Creatinine Ratio)
Previous medication history (within previous 12 months of index date)	
 • Anti-arrhythmics • Statins • Anti-platelets • Beta-blockers • ACE inhibitors • Anti-diabetic agents • Non-steroidal anti-inflammatory drugs (NSAIDs) • Antacids • Histamine receptor antagonists • Proton pump inhibitors (PPIs) • Disease-modifying anti-rheumatic drugs (DMARDs) • Antidepressants • Antipsychotic agents • Oral contraceptives

	
• Hormone replacement therapy (HRT)• Strong inhibitors of Cytochrome P450 or P-GP• Strong inducers of CYP3A4
Previous use of VKA (ever prior to index date)	
• Warfarin• Other Vitamin K antagonist(s)
Concurrent (from index date) co-medication	
• Anti-coagulants• Aspirin• Clopidogrel• Other

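### Section 9.3 gives conflicting look-back windows for medical history, smoking and BMI; the table's 12-month limit can understate past events in the primary baseline description

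*Protocol*

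**What the plan says.** Section 9.3 defines the variables twice, first in bullets and then in a parameter table.

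- **Table, diagnoses.** The block headed "Previous medical history (12 months prior to index date" lists acute MI, stroke or TIA, systemic peripheral arterial embolism, coronary artery disease, congestive heart disease, hypertension, diabetes, and renal disease by eGFR or ACR.
- **Bullets, scores.** CHADS2 and CHA2DS2-VASc are to be built from "presence/ history of congestive heart failure, hypertension, age, diabetes mellitus and prior stroke or transient ischaemic attack". HAS-BLED uses, among other items, "stroke history, prior major bleeding or predisposition to bleeding". Neither carries a time limit. The table's own row for the scores has no window.
- **Smoking and BMI.** The bullet says "smoking status, body mass index (BMI) and Townsend score: most recently recorded value before the index date". The table says "Smoking status (previous 6 months" and gives BMI the same 6 months.
- **Unlimited look-backs elsewhere.** The same table has "Previous use of VKA (ever prior to index date", and section 9.1 identifies "Patients with a record of Atrial fibrillation (AF) any time prior index date". Naive status in the 9.3 bullets also uses the whole prior record.

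Section 9.7 sends the analyst to all variables in section 9.3, so both sets of definitions apply. Nothing says which governs.

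**The concern.** Baseline characteristics are the first primary end-point (section 9.1.1), and the first primary objective contrasts them with clinical-trial patients (section 8.1). A 12-month window turns a history of stroke into a stroke record in the last year. Section 9.4 says Read codes capture diagnoses as reasons for each consultation, so an old stroke or MI that prompted no recent consultation can drop out. The cohorts could then look healthier than they are because of the window, and a larger sample would not correct that.

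The conflict also leaves the three risk scores without a settled definition. For smoking and BMI, a 6-month window can only add missing values compared with the latest-value rule. Section 9.6.1 expects missing values in a small proportion and gives them their own category, while section 9.9 concedes that these variables are not consistently recorded.

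**Working it through.** **Step 1: the two definitions side by side (section 9.3).**

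| Item | Bullets | Parameter table |
|---|---|---|
| Stroke/TIA, heart failure, hypertension, diabetes (score components) | history or prior event, no limit | 12 months |
| Acute MI, coronary disease | listed, no window | 12 months |
| Systemic embolism | not listed | 12 months |
| eGFR/ACR | eGFR before index, no length given | 12 months |
| Smoking, BMI | latest value before index | 6 months |
| Risk scores | history or prior event, no limit | no window |

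The direct contradictions concern the score components and smoking/BMI. For MI and coronary disease the bullets are silent, so the table is the only stated window. Table S2 in Annex 3, which defines renal impairment, gives no window. The table also writes congestive heart disease where the bullets write heart failure.

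**Step 2: direction.** Patients with a record in the last 12 months are a subset of those with any record before index. Prevalence under the 12-month rule is therefore equal or lower. The scores add points for conditions present, so a score built from the 12-month block is also equal or lower.

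**Step 3: size.** The protocol states no figure that depends on the window, so there is nothing to reproduce. Inputs, all assumed:

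- P, the share who ever had stroke/TIA: 10-30%.
- f, the share of those with a record in the last 12 months: 25-90%.
- Weight of stroke/TIA in CHADS2: 2 points (the usual weight; the protocol does not print it).

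Observed prevalence = P × f. Mean CHADS2 shortfall = 2 × P × (1 − f), if the score is built from the 12-month block.

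| P | f = 25% | f = 50% | f = 75% | f = 90% |
|---|---|---|---|---|
| 10% | 2.5%; 0.15 | 5%; 0.10 | 7.5%; 0.05 | 9%; 0.02 |
| 20% | 5%; 0.30 | 10%; 0.20 | 15%; 0.10 | 18%; 0.04 |
| 30% | 7.5%; 0.45 | 15%; 0.30 | 22.5%; 0.15 | 27%; 0.06 |

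Each cell gives observed prevalence, then mean CHADS2 shortfall. The extremes are 0.10 × 0.25 = 2.5% and 0.30 × 0.90 = 27% for prevalence, and 2 × 0.10 × 0.10 = 0.02 and 2 × 0.30 × 0.75 = 0.45 for the shortfall.

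**Step 4: against sampling error.** Section 9.5 cites an earlier CPRD study with 541 apixaban, 741 dabigatran and 1589 rivaroxaban naive users. These are not this study's sizes and serve only as a scale. At a true 20%, the 95% half-width 1.96 × √(0.2 × 0.8 / n) is 3.4, 2.9 and 2.0 percentage points respectively. With f = 50% the loss is 20 − 10 = 10 points, well above all three. With f = 90% it is 20 − 18 = 2 points, about the size of sampling error or smaller.

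**The case against.** Five points can be made on the other side.

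1. **The scores may be untouched.** A reader might infer that the 12-month limit lowers CHADS2, CHA2DS2-VASc and HAS-BLED outright. The documents do not support that: the limit sits on a different table row, the score row has no window, and the only text on how the scores are built sets no limit. This stands, so the effect on the scores is conditional. But scores built from the bullet would credit patients with a stroke that the comorbidity table does not show.

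2. **Bleeding history is not affected.** A reader might set the bullet on "haemorrhagic disease and history of intracranial haemorrhage, urogenital bleeding and gastrointestinal bleeding" against the table. Those items are not in the 12-month block, so they show no conflict. This stands.

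3. **The size is unknown.** The protocol gives neither P nor f, and coding diagnoses as consultation reasons leaves room for repeat coding. The loss is probably smaller for chronic conditions such as hypertension and diabetes. This stands, which is why only a wide assumed range is shown.

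4. **A fixed window has a merit.** Section 9.2 guarantees only one year of enrolment. A 12-month window observes everyone equally, whereas an any-time search depends on length of record, which may vary by calendar year and so touch the secondary time-trend objective. This is a real cost. But one year is a minimum rather than a cap, the protocol does not argue for the window on this ground, and it searches AF, VKA use and naive status without limit.

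5. **The study is descriptive and has a missing category.** True, but that category does not recover BMI or smoking values that the text's own rule would have used.

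**Conclusion.** The point holds as an internal contradiction that affects the first primary end-point. Confidence is high that the definitions conflict and that the 12-month rule can only lower prevalence or leave it unchanged. Confidence is low on the size.

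Under the assumed ranges above, stroke/TIA would show as 2.5-27% where 10-30% ever had it. The possible mean CHADS2 shortfall from this item is 0.02-0.45 points, and only if the score is built from the 12-month block. The bias ranges from about sampling error to several times that. MI is open to the same loss, which the documents do not allow to be quantified, and neither do they for the extra missing BMI and smoking values.

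Severity: should-fix. The study tests no hypothesis and the remedy is wording, but the windows need to be settled before the baseline tables and scores are programmed.

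**What to change.** In the section 9.3 parameter table:

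- Set the look-back for diagnoses and for all components of the three scores to any time up to the index date, and say so on the risk-score row.
- Keep a within-12-months line as an addition for acute events such as MI and stroke/TIA.
- For smoking and BMI, use the most recent value before index, as the bullet says, and report the age of the value.
- State one eGFR/ACR window and use it in the bullets, the table and Table S2.
- Use one term for heart failure.

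Report the length of prior record by cohort and calendar year, because any-time prevalence depends on it. The 12-month line then serves as a fixed-window check for acute events.

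The cost is a wording change plus a few extra table lines. The protocol already searches the whole prior record for AF, VKA use and naive status, so no new data source is needed.

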9.4 Data sources

THIN

Established in 2002, THIN now collects data from 570 practices, covering 6% of the general population, with more than 65 million patient-years of experience (CSD Medical Research, 2012). Eleven million individual patients are represented in the data; of those, approximately one-third are active at any one time. THIN records information on all services provided by the PCP, and information on specialist visits and hospitalizations are routinely forwarded to the PCP, who enters that information into the medical record. The population included in THIN is representative of the UK as a whole in terms of age, sex and geographic distribution (Bourke, Dattani et al. 2004; Blak, Thompson et al. 2011). THIN has been extensively validated for use in pharmacoepidemiology (Lewis, Schinnar et al. 2007).

The Read classification is used to code specific diagnoses as reasons for each consultation (O'Neil, Payne et al. 1995; Stuart-Buttle, Read et al. 1996), and a drug dictionary based on data from the MULTILEX classification is used to record prescriptions (First Data Bank 2014).

CPRD

The CPRD (<http://www.cprd.com/intro.asp>) contains diagnostic and prescribing information recorded by GPs as part of their routine clinical practice in the UK. The CPRD has information on 5.4 million individuals (active contributors), which represents approximately 9% of the UK population. These data are linkable, at least partially, with other health care data sets (e.g., hospitalization and national mortality data). Updated, valid, linked data are available through the CPRD Division of the UK Medicines and Health Care Products Regulatory Agency.

As in THIN, The CPRD also includes information recorded by GPs on patient demographics and lifestyle factors and detailed information on prescriptions written by the PCP. Free text comments are not available in CPRD.

The CPRD patients are representative of the UK population in terms of age and sex; it has been validated previously for use in pharmacoepidemiology to address a wide range of study questions in the European population (Herrett et al. 2015). Research at the CPRD requires approval from the CPRD Independent Scientific Advisory Committee (ISAC).

9.5 Study size

THIN version1605: The prevalence of AF (2011-2016), among patients 18+ and register with GP for at least a year 1.92% (No. of patients with AF= 75784). The prevalence of AF excluding patients with prior Mitral Stenosis or Valvular replacement = 1.89% (N= 74319).

CPRD GOLD database in 2014: authors reported a prevalence AF in all ages was 2.47% in men and 1.56 % in women. ([Bhatnagar](#) et al, 2015).

A study conducted using CPRD by Johnson et al, 2016, identified 541 na ĩve apixaban users, 1589 na ĩve rivaroxaban users, and 741 na ĩve dabigatran users up to October 2014.

9.6 Data Management

For each study project, all material including: study protocol, copy of Scientific Review Committee approval, algorithms and data collections, datasets, STATA programs, results from validation exercises and questionnaires, final STATA programs, and final report and publications are kept in one folder cross-shared by the CEIFE team. Monthly back-ups are performed and kept in a secure location, and all material is kept for a minimum of 10 years.

As a standard process, one researcher prepares the list of codes, test the computer algorithms to be used and runs statistical analysis after agreement on all phases of analyses with the rest of the team. As one measure of quality control, another researcher independently performs several checks in reviewing commands and analyses performed in order to minimise data errors.

9.6.1 Strategy for handling missing data

As a general strategy, no data imputation strategies will be applied to supplement missing data. The requirement for inclusion is complete data for critical variables; otherwise this individual is not eligible to be a member of the study population. However, missing values may occur in a small proportion. In this case, individuals with missing values will be kept in the analysis and a separate category will be created for missing values of that variable.

9.7 Data analysis

The analysis will be based on descriptive statistics: frequencies and percentages will be calculated to the variables of interests, continuous and count variables will be described using mean (\pm standard deviation), proportions, median (quartiles) and minimum and maximum values. 95% confidence intervals will be computed for descriptive variables. The following outcomes will be assessed:

- Describe the three study cohorts i.e. patients prescribed with rivaroxaban, dabigatran, apixaban by baseline characteristics, use of medications, comorbidities and healthcare utilization services

(see all the variables in section 9.3) among the three study cohorts and contrast them with the baseline characteristics of patients in clinical trials.

- Use of study medications: Dose at first Rx, dose posology, duration of treatment (time on index medication), discontinuation, switch to another study drug .
- To assess the proportion of patients that are dosed in accordance and non-accordance to label, in study population and in subset of patients with renal impairment
- Contrasting patient characteristics of those prescribed DOACs with the corresponding characteristics in patients participating in clinical trials.

Table 1: Dosing of each study drug in the study population.

	Rivaroxaban	Apixaban	Dabigatran
Low dose Renal impairment Other indication to reduce the dose Non- accordance to label			
Standard dose incl.documented renal impairment			
All			

- Use of medication before index date will be categorized as:
 - Concurrent use (when the drug supply lasts until index date or is prescribed at index-date)
 - Recent (when the drug supply ends 1-30 days before index date)
 - Past use (when the drug supply ends 31-365 days before index date)
 - Non-use: no use in year before index date

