9.1.1 Primary end-points

1. Baseline characteristics of NVAF patients in the UK prescribed any of the three direct oral anticoagulants (DOACs) (rivaroxaban, dabigatran and apixaban) for the first time for stroke prevention
2. Daily dose, dose posology, naïve status, treatment duration of DOACs for stroke prevention in NVAF patients including those with renal impairment

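### Treatment duration, part of primary endpoint 2, has only plain means and medians planned although enrolment runs to the end of data, so durations will be biased low

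*Protocol*

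**What the plan says.** - Protocol 9.1.1 makes duration part of the second primary endpoint: "Daily dose, dose posology, naïve status, treatment duration of DOACs for stroke prevention in NVAF patients including those with renal impairment".
- Protocol 9.7 sets the approach, "The analysis will be based on descriptive statistics", and then the form: "continuous and count variables will be described using mean" with SD, median with quartiles, minimum and maximum, plus 95% confidence intervals. The outcomes listed below it include "duration of treatment (time on index medication), discontinuation, switch to another study drug". No other method is named for these.
- Protocol 9.1 states that enrolment "extends from 1st January 2011 up to last available database extraction", which was May 2016 at the time of writing. Enrolment and data therefore stop together.
- Protocol 9.2 requires one year of registration and one year of recorded history, both before the index prescription. Nothing is required after it.
- Protocol 9.3 collects "healthcare utilization in the year prior to the index date and the year after", and medication use over the same two years.
- Section 9.6.1 (missing data) and section 9.9 (limitations) do not mention incomplete follow-up.

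**The concern.** A patient who starts shortly before the extraction and is still taking the drug has a known minimum time on treatment, not a known duration. If that minimum enters a mean or median as though it were complete, the summary describes the calendar as much as the prescribing. Describing duration is one of the study's primary purposes, and it is to be reported for three drugs and within renal impairment. Cohorts with different amounts of available follow-up would show different durations even if patients persisted equally on each drug.

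The year-after-index variables have a related problem. A late entrant has no full year after the index date, so raw counts of visits, admissions or co-medications would be too low unless the denominator is handled.

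**Working it through.** The protocol gives no duration figure to reproduce, so the check covers direction first and then size under stated assumptions.

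**Direction.** Let T be true time on drug and C the time from index to end of data. The observed value is min(T, C), which never exceeds T. If anyone is still on drug at C, the plain mean is too low whatever the shape of persistence, and shorter C means more censoring.

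**Inputs**
- Entry window from section 9.1: 1 January 2011 to 31 May 2016, 5.41 years × 12 = 64.95, about 65 months.
- Shorter window of 30 months: an assumption, standing for a cohort that entered use later.
- Persistence: assumed exponential, true median 24 months, the same in every cohort. λ = ln 2 / 24 = 0.02888 per month; true mean 1/λ = 34.6 months.
- Uptake: assumed even, P(C > t) = 1 − t/w, or rising linearly, P(C > t) = (1 − t/w)².

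**Formulas.** The plain median solves exp(−λt) × (1 − t/w)^k = 0.5, with k = 1 (even) or 2 (rising). With a = λw, the censored share is (1 − e^(−a))/a for even uptake and (2/a) × [1 − (1 − e^(−a))/a] for rising uptake. The plain mean is (1/λ) × (1 − censored share).

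**Substitution**
- w = 65, a = 1.877, e^(−a) = 0.153. Censored: even 0.847/1.877 = 0.451; rising (2/1.877) × 0.549 = 0.585.
- w = 30, a = 0.866, e^(−a) = 0.420. Censored: even 0.580/0.866 = 0.669; rising (2/0.866) × 0.331 = 0.764.
- Check of one median: at t = 15 with w = 65, exp(−0.433) × (1 − 15/65) = 0.648 × 0.769 = 0.499.

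| Window | Uptake | Censored | Plain mean (true 34.6) | Plain median (true 24) |
|---|---|---|---|---|
| 65 months | even | 45% | 19.0 | 15.0 |
| 65 months | rising | 58.5% | 14.4 | 11.1 |
| 30 months | even | 67% | 11.5 | 10.0 |
| 30 months | rising | 76% | 8.2 | 6.7 |

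**Spurious gap between cohorts with identical persistence**, same uptake pattern in both: even 15.0 − 10.0 = 5.0 months; rising 11.07 − 6.65 = 4.4 months.

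**Sensitivity to the true median**
- 12 months: even 9.3 − 7.2 = 2.1; rising 7.7 − 5.3 = 2.4.
- 36 months: even 18.5 − 11.3 = 7.2; rising 12.9 − 7.3 = 5.6.

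**By index year**, assuming 70% still on drug at 12 months (true mean 2.80 years, median 1.94): the plain mean falls from 2.32 years for 2011 to 1.38 for 2014, 0.77 for 2015 and 0.20 for 2016, with nothing truly changing. The plain median stays at 1.94 for 2011 to 2013 and then drops to 1.55, 0.76 and 0.19. The median is thus safe only where follow-up exceeds it.

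**Does the remedy work?** In the same 70% setting with the full window and even uptake, the plain median is 1.22 years and the Kaplan-Meier median is 1.94, matching the truth. Using completed episodes only gives 1.03, which is worse.

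**Year-after variables.** Share with under 12 months of potential follow-up: 65-month window, 12/65 = 18% (even) or 1 − (53/65)² = 34% (rising); 30-month window, 12/30 = 40% or 1 − (18/30)² = 64%.

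**The case against.** The strongest reply is that section 9.7 attaches no statistic to duration specifically. The sentence covers every continuous and count variable, Kaplan-Meier estimation is itself descriptive, and censoring rules usually sit in an analysis plan, which is not at hand. The protocol nowhere says that ongoing treatment will be counted as complete. This is fair, and a missing censoring rule alone would not be a finding. But the protocol does state how continuous variables will be summarised, lists time on drug among the outcomes, and offers nothing else for it. Followed as written, it yields a biased primary result.

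A second reply is that the study tests no hypothesis, and that section 9.9 urges care when reading the three cohorts. That caution concerns confounding, not follow-up, and the bias affects each cohort's own description. It is true that baseline characteristics, dose, posology, naïve status and renal function at index are untouched.

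Several stronger readings are tempting, and the documents do not support them:
- *The newest drug is the most affected.* No launch dates are given. Section 9.5 quotes naïve-user counts up to October 2014 (541 apixaban, 1589 rivaroxaban, 741 dabigatran), which show unequal numbers but not timing.
- *The time trends will be distorted.* The secondary objective concerns the characteristics of first-time use, which may mean features at initiation only. Trends suffer only if duration or post-index variables are among those trended.
- *The gap could reach 8 months at a 24-month median.* That subtracts 6.7 (rising uptake) from 15.0 (even uptake). Like for like it is 4.4 to 5.0.
- *Duration at death is truncated too.* Death ends treatment, so that duration is complete.

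**Conclusion.** The concern holds for treatment duration. Open enrolment to the end of data, no required follow-up and a plain mean or median together give durations that are too low, the more so where follow-up is shorter. The mean is low under any persistence pattern in which some patients are still on drug at the end of data. The median is low unless follow-up comfortably exceeds it.

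The size is illustrative. With exponential persistence and a true median of 24 months, the plain median is 15.0 or 11.1 months over the 65-month window. The spurious difference against an assumed 30-month cohort is about 4.4 to 5 months; it is about 2 months if the true median is 12, and about 6 to 7 if it is 36. Neither the persistence, the uptake pattern nor the 30-month window comes from the protocol, so these figures do not rank the three drugs.

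The year-after-index variables share the weakness but are secondary: section 9.3 lists them without fixing an estimator.

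**What to change.** In section 9.7, take duration out of the generic summary and specify:
- Kaplan-Meier persistence, or cumulative incidence of stopping, with censoring at transfer-out, last data collection and study end.
- Death and switch as ends of index treatment, or as competing events, with the choice stated because it defines the quantity estimated.
- Estimates with 95% confidence intervals by drug at fixed horizons, for example 6 and 12 months.
- Any comparison by index year only at a horizon that every year reaches.

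For the year-after-index variables in section 9.3, either restrict to patients with at least 12 months of potential follow-up or report rates per person-year.

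The cost is a few sentences and standard survival commands in Stata, which section 9.6 shows is already in use. The one downside is that the latest initiators drop out of the fixed 12-month tables or appear there as rates.

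### Time on index drug, part of a primary end-point, is right-censored, but section 9.7 gives only plain summaries for it and for discontinuation and switch

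*Protocol*

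**What the plan says.** Section 9.1.1 of the Protocol makes treatment duration part of the second primary end-point: "Daily dose, dose posology, naïve status, treatment duration of DOACs for stroke prevention in NVAF patients including those with renal impairment". The second and third primary objectives in section 8.1 also include it.

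Section 9.7 sets out the analysis: "The analysis will be based on descriptive statistics: frequencies and percentages will be calculated to the variables of interests". It adds that "continuous and count variables will be described using mean" with standard deviation, proportions, "median (quartiles) and minimum and maximum values", and that 95% confidence intervals will be computed. The outcomes it then lists include "duration of treatment (time on index medication), discontinuation, switch to another study drug".

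On entry and follow-up, section 9.1 says: "The study enrollement period extends from 1st January 2011 up to last available database extraction", which was May 2016 when the Protocol was written. The one-year requirements in section 9.2 (enrolment with the practice, time since first recorded contact) both look back from the index prescription. Nothing requires any time after it. No section defines the end of follow-up, mentions censoring, or sets a fixed horizon for duration, discontinuation or switch. The missing-data rule in section 9.6.1 (no imputation, a separate missing category) does not cover incomplete follow-up, and the limitations in section 9.9 do not mention it.

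**The concern.** A patient who starts a drug one month before extraction can be observed on it for at most one month, however long treatment lasts. Because entry stays open until the data end, every cohort will contain such patients. The recorded value is the shorter of true time on drug and available follow-up. A mean, median or maximum of those values describes a mixture of the two, and summarising only the patients who stopped shortens the figure further.

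A crude percentage who discontinued or switched has the matching defect: it is the share observed to stop by whenever each record happens to end, so it answers no question about a stated period.

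At stake are the duration figures for each drug and for the renal-impairment subset. If start dates differ between drugs, or if duration is examined by calendar year of start under the secondary objective, a difference in follow-up can pass for a difference in use. The result can also look incoherent: the later-started drug would appear to be used for less time and yet be stopped less often.

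**Working it through.** The Protocol gives no duration or persistence figure, so there is nothing of its own to reproduce. The direction of the error follows from the design; its size has to be illustrated.

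**Direction.** With true time on drug T and available follow-up C, the observed time is min(T, C), which never exceeds T. Plain summaries of observed time therefore cannot overstate duration, whatever the stopping pattern.

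**Inputs.**
- From section 9.1: entry from 1 January 2011 to May 2016, which is 5 × 12 + 5 = 65 months.
- Assumed: constant stopping rate r, with persistence at 12 months p of 0.70 (range 0.60 to 0.80).
- Assumed: entry uniform over the last W months before extraction, so C is uniform on (0, W). W = 65 is the full window; W = 24 stands for a cohort that started late.

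**Formulas.**
- r = −ln(p)/12
- true median = ln 2 / r
- crude median m solves exp(−r·m) × (1 − m/W) = 0.5
- crude proportion discontinued = 1 − (1 − exp(−r·W))/(r·W)

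**Central case, p = 0.70.** r = 0.3567/12 = 0.02972 per month, so the true median is 0.6931/0.02972 = 23.3 months.
- W = 65: r·W = 1.932 and exp(−1.932) = 0.1449. Crude discontinued = 1 − 0.8551/1.932 = 55.7%. Crude median 14.7 months (check: 0.646 × 0.774 = 0.50).
- W = 24: r·W = 0.7133 and exp(−0.7133) = 0.490. Crude discontinued = 1 − 0.510/0.7133 = 28.5%. Crude median 8.5 months (check: 0.776 × 0.644 = 0.50).

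**Range, by the same formulas.**

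| Persistence at 12 months | True median (months) | Crude median, W = 65 | Crude median, W = 24 | Crude discontinued, W = 65 / W = 24 |
|---|---|---|---|---|
| 60% | 16.3 | 11.6 | 7.5 | 66% / 37% |
| 70% | 23.3 | 14.7 | 8.5 | 55.7% / 28.5% |
| 80% | 37.3 | 18.9 | 9.6 | 42% / 19% |

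Within each row persistence is identical; only the entry window changes.

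**Would a censoring-aware estimate repair it?** A separate simulation (200,000 patients per scenario, exponential stopping, true median 2 years, true mean 2.89 years, uniform entry over 5.41, 4, 3 or 2 years) gave:
- plain means of 1.58, 1.32, 1.09 and about 0.80 years;
- a mean of 1.32 years among those who stopped, for the longest window;
- Kaplan-Meier medians of 2.00, 2.00, 2.01 and not reached;
- Kaplan-Meier one-year persistence of 0.71 in all four, against a true 0.707.

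The Kaplan-Meier results do not depend on the entry window; the plain summaries do.

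**The case against.** **The opening of section 9.7 is generic.** It covers every variable and no sentence says how time on index medication is computed. A Kaplan-Meier median is itself descriptive, and a statistical analysis plan, not available here, could specify one. Part of this stands: the fair statement is that the Protocol makes no provision for censoring, not that it rules out a suitable method. But section 9.7 names the mean, standard deviation and maximum, which do not suit censored times, and the ENCePP checklist in Annex 2 marks the choice of statistical techniques as described. This is more than detail left for later.

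**Duration could mean prescription length.** Section 9.3 mentions pack size beside duration of treatment, and the length of a prescription is not censored. Section 9.7, however, explains duration as time on the index medication.

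**Only duration is primary.** This stands. Discontinuation and switch appear in the analysis lists but in no objective or end-point, and no hypothesis is to be tested. It lowers the weight of the point.

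Three stronger readings are tempting and are not supported:
- A reader might infer that the drugs will look different because of follow-up. The Protocol gives no start dates by drug, so neither the size nor the direction of such a distortion can be derived. It is conditional.
- A reader might take the section 9.4 remark on THIN patients, "of those, approximately one-third are active at any one time", as a measure of loss. It describes everyone represented in that database and gives no loss rate for these cohorts.
- A reader might infer, because section 9.3 lists no death, transfer-out or last-collection date, that the end of a record cannot be told from stopping the drug. Section 9.3 lists analysis variables, eligibility already relies on registration data, and section 9.4 says CPRD is at least partly linkable to national mortality data. Absence from the list does not show that the dates are unavailable.

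**Conclusion.** The point holds. Entry up to extraction with no required follow-up makes time on index drug right-censored, and the summaries that section 9.7 names understate it. Discontinuation and switch percentages without a horizon cannot be interpreted.

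The downward direction for duration needs no assumption; the size does. Under exponential stopping, uniform entry and 70% persistence at 12 months, the crude median falls short of the true one by 23.3 − 14.7 = 8.6 months with 65-month entry and by 23.3 − 8.5 = 14.8 months with 24-month entry. The 24-month window is illustrative and is not a property of any of the three drugs.

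This should be fixed. One component of a primary end-point is affected, the study is descriptive, and the repair is cheap.

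**What to change.** In section 9.7:

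1. Define the end of follow-up (transfer-out, the practice's last data collection, study end), and list the dates needed.
2. State how death is handled for time on drug: whether it ends treatment or censors it.
3. State the prescription-gap rule that defines discontinuation. Without it no estimate of persistence can be computed from prescription records.
4. Replace the plain summaries of time on index drug with Kaplan-Meier estimates: the median if reached, and persistence at fixed times such as 12 months with 95% confidence intervals, by drug and in the renal-impairment subset.
5. Report discontinuation and switch as cumulative incidence at the same fixed times, treating each other and death as competing events.
6. Report the length of follow-up in each cohort.

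The cost is Protocol wording and a little more analysis work, with no new patients. The downside is that the median may be reported as not reached in a late-starting cohort; persistence at a fixed time would still be available there, provided follow-up extends to that time.
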